6.3.5.3. Counting rules for occurrences of solicited events

When the occurrences of solicited events are summarized, each event recorded as having occurred during a specific period will be counted as only one occurrence regardless of the number of days on which it occurs.

6.3.5.4. Intensity grading for solicited events

Unless otherwise specified, the intensity for solicited events are as per GSK grading scale.

The intensity of administration site erythema/swelling, and fever will be scored as per GSK grading scale and China grading scale as follows:

GSK Grading Scale		
Intensity grade	Erythema/Swelling	Fever (by any measurement)
0	≤20 mm	< 38.0°C
1	>20 - ≤50 mm	≥38.0°C – ≤38.5°C
2	>50 - ≤100 mm	>38.5°C – ≤39.0°C
3	>100 mm	>39.0°C
China Grading Scale *		
Intensity grade	Erythema/Swelling	Fever (by axillary measurement)
0	< 25 mm	<37.3°C
1	25 - <50 mm	37.3°C - <38.0°C
2	50 - <100 mm	38.0°C - <38.5°C
3	≥100 mm	≥38.5°C
4	Abscess, exfoliative dermatitis, and dermis or deep tissue necrosis **	≥39.5 and persistent for more than 3 days

* According to the Chinese guidelines [Grading Criteria for Adverse Events in Clinical Trials of Preventive Vaccines (draft version) issued by NMPA in 2025].

** It will not be derived in the analysis given the solicited events eCRF data are based on GSK grading scale.

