**Amendment 1 (15 Feb 2024)****Overall rationale for the current Amendment:**

The protocol is amended based on feedback received from Notice of Drug Clinical Trial Approval issued by Center for Drug Evaluation (CDE), National Medical Products Administration (NMPA):

- It is recommended to conduct efficacy surveillance (as secondary endpoints) in the study.
- It is recommended to conduct safety evaluation as per Chinese guidelines (Grading Criteria for Adverse Events in Clinical Trials of Preventive Vaccines) and record events of atrial fibrillation (AF) as Adverse Events of Special Interest (AESIs).

In addition, the total sample size of the study population is increased from 1500 to 2600 based on a sensitivity analysis of study power.

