**Table 22 Intensity scales for solicited events in participants in China**

Event	Intensity grade	Parameter
Pain at administration site	0	None
	1	Mild: Any pain neither interfering with nor preventing normal everyday activities.
	2	Moderate: Painful when limb is moved and interferes with everyday activities.
	3	Severe: Significant pain at rest. Prevents normal everyday activities.
Erythema at administration site		Greatest surface diameter in mm
Swelling at administration site		Greatest surface diameter in mm
Temperature*		Temperature in °C
Headache	0	None/Normal
	1	Mild: Headache that is easily tolerated
	2	Moderate: Headache that interferes with normal activity
	3	Severe: Headache that prevents normal activity
Fatigue (tiredness)	0	None/Normal
	1	Mild: Fatigue that is easily tolerated
	2	Moderate: Fatigue that interferes with normal activity
	3	Severe: Fatigue that prevents normal activity

Event	Intensity grade	Parameter
Myalgia (muscle pain)	0	None/Normal
	1	Mild: Myalgia present but does not interfere with activity
	2	Moderate: Myalgia that interferes with normal activity
	3	Severe: Myalgia that prevents normal activity
Arthralgia (joint pain)	0	None/Normal
	1	Mild: Arthralgia present but does not interfere with activity
	2	Moderate: Arthralgia that interferes with normal activity
	3	Severe: Arthralgia that prevents normal activity

\*Refer to the SoA (Section 1.3) for the definition of fever and the preferred location for temperature measurement

The maximum intensity of administration site redness/swelling, and fever will be scored at GSK as follows:

Intensity grade	Erythema/Swelling	Fever
0	≤20 mm	<37.3°C
1	>20 - ≤50 mm	≥37.3°C - <38.0°C
2	>50 - ≤100 mm	≥38.0°C - <38.5°C
3	>100 mm	≥38.5°C

\*Fever is defined by axillary route as per Chinese guidelines [[Grading Criteria for Adverse Events in Clinical Trials of Preventive Vaccines](#) issued by NMPA in Dec 2019].

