4.8. Changes to Protocol Defined Analyses

A blinded safety analysis was conducted using data of 11Mar2025 to support the CDE consultation of RSV OA=ADJ-028 study.

There were no other changes or deviations to the originally planned statistical analysis specified in the protocol amendment 1 (Dated: 15 Feb 2024).

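### The SAP's default fever scale differs from the protocol's only solicited-fever scale, never grades higher, is not declared in SAP 4.8, and governs every solicited table that names no scale

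*SAP*

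**What the plan says.** **Protocol.** Section 10.3.5.2 (Table 22 and the grid beneath it) has a single scale for fever as a solicited event, introduced by "The maximum intensity of administration site redness/swelling, and fever will be scored at GSK as follows". Grade 0 is below 37.3 °C, grade 1 is "≥37.3°C - <38.0°C", grade 2 runs from 38.0 to below 38.5 and grade 3 is 38.5 or above. The footnote fixes the route and source: "Fever is defined by axillary route as per Chinese guidelines", citing the December 2019 document.

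**SAP.** Section 6.3.5.4 sets the default: "Unless otherwise specified, the intensity for solicited events are as per GSK grading scale". On that scale fever grade 0 is below 38.0 °C, grade 1 is "≥38.0°C – ≤38.5°C", grade 2 is above 38.5 up to 39.0 and grade 3 is above 39.0, whatever the route. The same section says that "fever will be scored as per GSK grading scale and China grading scale as follows" and sets out a China scale for axillary readings. Its fever grades 0 to 3 have the protocol cut-offs, a grade 4 is added, and it cites a 2025 draft of the guideline. Section 6.3.8.2 converts oral to axillary (minus 0.2 °C) for the China grading only.

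**Where each scale applies.** SAP 4.3.3.1 names both scales for one output, the half-degree fever table. It names none for the any-grade and grade 3 rows of individual events, any systemic event and any solicited event. SAP 4.3.3.3 (pooled tables) and 6.3.5.2 (durations and grade 3 days) name none either.

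**Declared changes.** After reporting one blinded safety analysis, SAP 4.8 says: "There were no other changes or deviations to the originally planned statistical analysis specified in the protocol amendment 1".

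**The concern.** Solicited systemic events in the two China groups are a listed secondary endpoint (Protocol Table 7), and fever is one of them. Part of the rationale for Amendment 1 was the regulator's advice: "It is recommended to conduct safety evaluation as per Chinese guidelines". If the main solicited tables grade fever on a scale that the protocol does not contain, with higher thresholds, the reported any-grade and grade 3 rates cannot exceed those the protocol definition would give, and may fall short of them. A reader who relies on SAP 4.8 would not know that the definition had moved.

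**Working it through.** There is no planned sample size, power or alpha to reproduce here. The check is a comparison of cut-offs.

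**1. Grade by temperature.** Each reading from 36.5 to 40.4 °C in steps of 0.1 was graded on the protocol scale and on the SAP default. Axillary readings were used as they stand. Oral readings were left unconverted for the SAP default (any route) and reduced by 0.2 °C for the protocol scale.

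| Axillary reading (°C) | Protocol grade | SAP default grade |
|---|---|---|
| below 37.3 | 0 | 0 |
| 37.3–37.9 | 1 | 0 |
| 38.0–38.4 | 2 | 1 |
| 38.5 | 3 | 1 |
| 38.6–39.0 | 3 | 2 |
| 39.1 and above | 3 | 3 |

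For oral readings the default is lower at 37.5–37.9 (1 to 0), 38.2–38.5 (2 to 1) and 38.7–39.0 (3 to 2), and equal elsewhere, including 38.0–38.1 and 38.6. On neither route is the default ever higher.

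**2. Route dependence.** By the SAP's own conversion, an axillary 37.9 is an oral 37.9 + 0.2 = 38.1. On the default scale the oral reading is grade 1 and the axillary reading is grade 0.

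**3. Which rows are affected.** SAP 6.3.5.1 counts a participant under any grade if a grade 1, 2 or 3 occurs, or if the event is marked present and a daily recording is missing. With complete recordings, an axillary peak of 37.3–37.9 is therefore not counted as fever. For duration, 6.3.5.2 requires at least one day above grade 0, so the same participant has no fever duration. Days at 38.5–39.0 axillary do not count as grade 3 days.

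**4. Which rows are not affected.** The SAP default diameters for erythema and swelling (20, 50 and 100 mm) equal the protocol's, so the administration-site composite does not change. It is the SAP China scale that differs there: grade 1 starts at 25 mm.

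**5. Illustrative size.** The China vaccine group is 1800 × 2/3 = 1200. Let q be the share whose maximum axillary temperature is 37.3 to below 38.0, and c the share of those who also have another solicited systemic event. Neither figure is in the documents; both are assumed.

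- Loss from the any-fever row: 1200 × q. At q = 1% this is 12; at q = 10% it is 120.
- Loss from any solicited systemic event: 1200 × q × (1 − c).

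| q | c = 0 | c = 0.3 | c = 0.6 | c = 0.9 |
|---|---|---|---|---|
| 1% | 12 | 8 | 5 | 1 |
| 3% | 36 | 25 | 14 | 4 |
| 5% | 60 | 42 | 24 | 6 |
| 10% | 120 | 84 | 48 | 12 |

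The composite loss thus runs from 0.1 to 10 percentage points (1 to 120 participants). For any solicited event it is no larger, because a site event also keeps the participant in the count.

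**The case against.** The strongest reply is that fever on the protocol definition is already planned. SAP 6.3.5.4 scores fever on both scales, 4.3.3.1 tabulates it on both, and the China grades 0 to 3 use the protocol thresholds with oral readings converted. Any-grade and grade 3 fever at 37.3 and 38.5 °C should therefore be recoverable from that table. This stands. A reader might infer that the SAP under-counts fever throughout, or drops the evaluation by Chinese criteria; the documents do not support either.

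Second, the protocol endpoint is each solicited event. The composites and pooled tables first appear in the SAP, and Protocol 9.3 leaves descriptive safety analyses to it. So there is no protocol composite rate to fall below. This also stands, but it does not explain why composites containing fever should rest on a definition of fever that the protocol lacks. Nor can the half-degree table rebuild them, since it does not show who had other events.

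Third, a reader might take SAP 4.8 as a specific denial that grading changed. It is a general sentence that does not mention grading; the fault is omission. The guideline version differs as well, but fever grades 0 to 3 are the same under both citations, so no fever result changes through that.

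Finally, both China groups are graded alike, nothing is tested on these endpoints and the co-primary decision is untouched. That bears on severity. It does not make the effect cancel: the between-group difference in any fever shifts by the difference between the groups' q values, which is zero only if those are equal.

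**Conclusion.** The point holds in a limited form. The default cut-offs conflict with the protocol's solicited-fever scale, and the SAP does not say so. The consequence is confined to outputs that name no scale: the individual fever rows, the systemic and overall composites, the pooled tables, and fever duration and grade 3 days. In these, grades can only be equal to or lower than the protocol's. A composite row changes only for participants who have no other event that qualifies for that row.

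The size cannot be fixed, because neither document gives a fever rate, the split between oral and axillary readings, or the overlap of fever with other events. The range of 1 to 120 of 1200 rests wholly on the assumed q (1% to 10%) and c (0 to 0.9) and on axillary readings with complete daily recordings. That fever can be recovered from the half-degree table assumes that its China-scale version shows the 37.3 and 38.5 °C cut-offs; the layout is not given.

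Severity: should-fix, since the endpoint is secondary and descriptive and fever also appears on the protocol cut-offs.

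**What to change.** Reconcile Protocol 10.3.5.2 with SAP 4.3.3.1, 4.3.3.3, 4.8, 6.3.5.2 and 6.3.5.4:

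- In SAP 6.3.5.4, make the protocol fever cut-offs (axillary, oral readings reduced by 0.2 °C) the default for the individual fever, any systemic, any solicited, pooled and duration tables. Show the 38.0/38.5/39.0 °C scale as supplementary. The lesser option is to keep the present default and add protocol-scale rows to each of these tables.
- Limit the change to fever. Erythema and swelling already follow the protocol under the present default, and moving them to the China scale would create a new mismatch.
- In SAP 4.8, list the difference in fever scale and the change from the December 2019 guideline to the 2025 draft, or return to the version that the protocol cites.

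The cost is SAP wording, a grading flag and some extra programming. Temperature is already recorded in °C, so no new data are needed. The reported fever rates may be less favourable.

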6.3.6. Unsolicited adverse events

Unsolicited adverse event summaries are including serious adverse events unless specified otherwise.

As per CDISC Vaccines Therapeutic Area guide, the solicited events which continue beyond the observation period are stored in the Adverse Events (AE) domain, but they do not contribute to the summaries of unsolicited adverse events.

Missing severity, relationship with study vaccine, and outcome of unsolicited adverse events will not be replaced and will appear as 'UNKNOWN' when displayed in a statistical output.

6.3.7. Pooling of solicited and unsolicited adverse events

Unsolicited adverse events with missing administration site flag will be considered systemic.

Solicited events will be coded by MedDRA as per the following codes:

Solicited event	Lower level term code	Corresponding Lower level term decode
Pain	10022086	Injection site pain
Redness (Erythema)	10022061	Injection site erythema
Swelling	10053425	Injection site swelling
Fever	10016558	Fever
Headache	10019211	Headache
Fatigue	10016256	Fatigue
Myalgia	10028411	Myalgia
Arthralgia	10003239	Arthralgia

Note that these codes might be adapted depending on the current version of MedDRA at the time of analysis.

Multiple events with the same preferred term which start on the same day are counted as only one occurrence.

6.3.8. Data derivation

6.3.8.1. Age at vaccination

Age will be calculated from date of birth and the date of study intervention, and rounded down to integers, i.e. age at vaccination = FLOOR[(date of study intervention - date of birth + 1)/365.25], where FLOOR is the SAS function to round down a decimal number to integer. Partial date will be imputed.

Given only year of birth is collected, if a derived age is equal to 59 and the participant has no any violation to the ≥ 60 YOA inclusion criterion (i.e. INC#1 in protocol 5.1), the derived age is considered as 60.

6.3.8.2. Temperature

Temperatures will be presented in degrees Celsius (°C). For China grading temperatures reported in oral measurement will be converted as follows:

$$\text{Axillary temperature (°C)} = \text{oral temperature} - 0.2 \text{ (°C)}$$

6.3.8.3. Frailty status

The frailty status at baseline will be classified to frail, pre-frail and fit as per the Gait speed test:

Frailty Status	Definition
Frail	Participants with a walking speed <0.4m/s or who were not able to perform the test*
Pre-Frail	Participants with a walking speed between 0.4-0.99 m/s
Fit	Participants with a walking speed ≥ 1 m/s

* Participants who were not able to perform the test for the following reasons in the eCRF: Tried but unable, Could not walk unassisted, Not attempted – study staff or participant felt unsafe, participants unable to understand the instructions

6.3.8.4. Numerical serology results

Numerical serology results will be derived from the content of IS.ISORRES in the SDTM dataset. For assays with a specific cut-off, the following derivation rules apply:

IS.ISORRES in SDTM	Derived value
“NEG”, “-“, or “(-)”	cut-off/2
“POS”, “+”, or “(+)”	cut-off
“< value” and value is \leq assay cut-off	cut-off/2
“< value” and value is $>$ assay cut-off	value
“> value” and value is $<$ assay cut-off	cut-off/2
“> value” and value is \geq assay cut-off	value
“value” and value is $<$ cut-off	cut-off/2
“value” and value is \geq cut-off and value is \leq ULOQ	value
“value” and value is $>$ ULOQ	ULOQ
All other cases	missing

6.3.8.5. Geometric mean titers (GMTs) and concentrations (GMCs)

GMT calculations are performed by taking the inverse logarithm of the mean of the log titre or concentration transformations. Non quantifiable neutralizing titres will be converted as described in Section 6.3.8.4 for the purpose of GMT calculation. Cut-off values are defined by the laboratory before the analysis.

6.3.9. Display of decimals

6.3.9.1. Percentages

Percentages and their corresponding confidence limits will be displayed with one decimal except for 100% in which case no decimal will be displayed.

6.3.9.2. Demographic/baseline characteristics statistics

The mean, median, and standard deviation for continuous baseline characteristics (height, weight, BMI, pre-dose body temperature) will be presented with one decimal.

The minimum and maximum values and quartile values (if required) will be presented with the same number of decimals as the observed values.

The maxima and minima of transformed height/weight variables will be displayed with 0 and 1 decimal respectively.

The maximum and minimum of transformed body temperatures will be displayed with one decimal.

6.3.9.3. Serological summary statistics

For each assay, GMTs and their confidence limits will be presented with one decimal, as well as GMT fold increase from pre-vaccination.

GMT group ratios and their confidence limits will be displayed with 2 decimals regardless of the actual values.

6.3.10. Trademarks

Trademarks of the GlaxoSmithKline Group of Companies
AREXVY

Trademarks not owned by the GlaxoSmithKline Group of Companies
SAS

